The main purpose of this study is to collect information on various aspects of feasibility and not efficacy of treatment, therefore we contend that a priori matching or a priori stratification is not relevant in this case. We have also considered another challenging feature of the design; caregivers and AD patients will interact. Participants may also interact with one another directly in their groups. This interaction creates the expectation that some level of intraclass correlation (ICC) will develop such that AD patient and caregiver responses to treatment will be positively correlated. The magnitude of the ICC depends on the type, duration, and intensity of these interactions, and are currently unknown. That ICC may be negligible at baseline, but it can develop over the course of the trial. We contend that with a limited number of treatment cohorts (2), and the limited number of yoga teachers (1-2) we have very limited ability to estimate the ICC, or the component of variance associated with the group or yoga teacher. Again, the main purpose of this study is to collect information on various aspects of feasibility and ICC is of negligible importance in our design, and a priori matching or a priori stratification is not necessary in this case.

Month											
1	2	3	4	5	6	7	8	9	10	11	12
Recruit AD & Caregiver (n=5 pairs)			Treat AD & Caregivers one-on-one format			Treat AD & Caregivers group format			Data analysis, manuscript submission and funding application		
			Run AD & Caregiver pairs (n=10 pairs)								

Table 1. Recruitment Table

Statistical Plan and Data Analysis

The main analytic strategy will be descriptive statistics for pre- and post-intervention assessments for AD patients and their caregivers. For feasibility of retention and adherence, we aim to reach at least 65% retention. For feasibility of treatment fidelity, we will aim for $\geq 95\%$ of treatment components. For the outcomes that will be measured repeatedly (i.e., both at baseline

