and post-treatment), we will estimate how they change over time (pre to post). Note that some of the assessment measures used are used only for AD patients or caregivers. The results will be reported for both groups separately. Accordingly, in terms of AD patient outcomes, we will estimate changes in pain (DVPRS), depression (BDI-II), sleep (PSQI) and cognition (CanTab). These results will provide preliminary data on target engagement and therefore will inform and shape the future trial in terms of elucidating the mechanism of action. For the caregiver measures, we will estimate changes in caregiver burden (Revised Memory and Behavior Problems Checklist), quality of life (SF-36), depression (BDI-II), and sleep (PSQI). We will also explore the relationship between changes in patient outcomes and their caregiver outcomes. For all analyses regarding changes in outcomes, we will first employ simple paired t-test (pre vs. post) given the correlation between pre and post measures. We will also estimate changes based on longitudinal mixed effects modeling using maximum likelihood estimation. We will put in rigorous effort to minimize missing data. Nonetheless, we expect some attrition by post intervention assessment. In our mixed effects modeling, data points that are missing due to attrition or missing assessment will be handled assuming that data are missing at random conditional on observed information. In all statistical analyses, we will focus on collecting preliminary data on clinical significance (i.e., effect size) instead of making formal inference (i.e., p-value).

Inclusion/Exclusion Criteria

Inclusion Criteria for AD patients (As determined by):

- Diagnosis of probable Alzheimer's disease- Baseline
- Mini-Mental State Examination (MMSE) score 18-25 (Mild AD) (screening interview) \geq 18 years old
- Has a primary care provider who can provide medical clearance for participation in the study
- Diagnosis of chronic musculoskeletal pain $>$ 6 months
- Minimum pain intensity at screening visit: pain rated \geq 4 on a 0-10 Numeric Rating Scale (NRS)
- Not begun new pain treatments or medications in the past month
- If on a psychotropic medication regimen: stable regimen for at least 4 weeks prior to entry to the study; willingness to remain on a stable regimen during the 12-week acute treatment phase
- English literacy
- Wireless internet connection at home (Screening interview)

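### The plan does not say which pre-post estimate is carried forward, and it fits its mixed model by maximum likelihood, which understates variance at 15 per role

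*Combined protocol and SAP*

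**What the plan says.** Under Statistical Plan and Data Analysis, the overall approach is descriptive: "The main analytic strategy will be descriptive statistics for pre- and post-intervention assessments for AD patients and their caregivers". For every analysis of change, "we will first employ simple paired t-test (pre vs. post) given the correlation between pre and post measures". The next step is "We will also estimate changes based on longitudinal mixed effects modeling using maximum likelihood estimation". Patients and caregivers are reported separately.

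On missing data the section says "Nonetheless, we expect some attrition by post intervention assessment". Missing values in the mixed model are to be "handled assuming that data are missing at random conditional on observed information". No handling is given for the t-test, and no imputation is mentioned. On retention, "we aim to reach at least 65% retention".

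On the use of the results, "we will focus on collecting preliminary data on clinical significance (i.e., effect size) instead of making formal inference". Study Design says that the 15 dyads are to inform a later, fully powered efficacy trial.

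The section does not state which of the two estimates is taken forward if they differ, the covariance structure of the mixed model, or any small-sample degrees-of-freedom method.

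**The concern.** There are two separate matters.

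**Which estimate is used.** The t-test drops anyone without a post-treatment visit. It is unbiased for the enrolled group only under stronger conditions than the missing-at-random assumption that the plan adopts for its mixed model. The mixed model can keep those participants' baseline values. If the two disagree, nothing says which one goes into the planning of the next trial.

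**How the mixed model is fitted.** ML does not allow for the estimated means when it estimates variances. In large samples this is negligible. With at most 15 people per role it makes the variance of change, and hence the error bars, too small.

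At stake are the size of the change and its SD as planning inputs. No decision within this study depends on them.

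**Working it through.** The plan states no SD, correlation, effect size or dropout pattern for these analyses, so there is no figure of its own to reproduce.

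**Inputs from the document.** 15 patients and 15 caregivers (Study Design); retention aim 65% (Statistical Plan and Data Analysis).

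**Assumptions.** Pre-post correlation r = 0.3, 0.5 or 0.7. Ratio of post SD to baseline SD k = 1 or 1.3. Log-odds of dropout rising by s = 0, 0.5 or 1 per baseline SD of worse score.

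**1. Pairs available.** 0.65 × 15 = 9.75, about 10 per role.

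**2. Effect of ML on the variance, complete pairs.** ML gives (n − 1)/n times the unbiased variance of change.
- n = 15: 14/15 = 0.933, 7% low; standard error factor √0.933 = 0.966.
- n = 10: 9/10 = 0.900, 10% low; standard error factor √0.900 = 0.949.

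A complete simulated data set of 15 pairs gave a standard error of 0.2881 by both the paired t-test and REML, and 0.2783 by ML: 0.2783/0.2881 = 0.966, as expected.

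**3. Effect of ML with dropout.** In simulated unstructured fits with 15 enrolled, the ML variance of change was 5 to 8% below the true value. At 65% retention and s = 1:

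| r | Mean ML SE | Mean REML SE | ML/REML | Actual SD of the estimate | ML/actual | REML/actual |
|---|---|---|---|---|---|---|
| 0.3 | 0.327 | 0.344 | 0.95 | 0.390 | 0.84 | 0.88 |
| 0.5 | 0.282 | 0.297 | 0.95 | 0.338 | 0.83 | 0.88 |
| 0.7 | 0.222 | 0.234 | 0.95 | 0.274 | 0.81 | 0.85 |

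REML recovers about 5%. The rest of the shortfall arises because the model treats its estimated covariance as known, which is why REML alone is not enough and a small-sample adjustment is needed.

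**4. Bias of the completers-only estimate.** Set the baseline to mean 0 and SD 1. Given baseline x, the expected change differs from the overall mean change by (k·r − 1)·x. Hence

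bias = (k·r − 1) × E[x | completer].

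With the logistic intercept solved for 65% retention, E[x | completer] = −0.166 at s = 0.5 and −0.292 at s = 1. For example, k = 1, r = 0.3, s = 1: (0.3 − 1) × (−0.292) = 0.20.

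| Case (65% retention) | r = 0.3 | r = 0.5 | r = 0.7 |
|---|---|---|---|
| k = 1, s = 0.5 | 0.12 | 0.08 | 0.05 |
| k = 1, s = 1 | 0.20 | 0.15 | 0.09 |
| k = 1.3, s = 0.5 | 0.10 | 0.06 | 0.01 |
| k = 1.3, s = 1 | 0.18 | 0.10 | 0.03 |
| One SE, 10 pairs, k = 1 | 0.37 | 0.32 | 0.24 |
| One SE, 10 pairs, k = 1.3 | 0.44 | 0.37 | 0.29 |

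The standard error is √((1 + k² − 2kr)/10). Units are baseline SDs. On a scale where higher is worse, positive bias understates improvement; if those with better baseline scores dropped out instead, the sign would reverse. With k = 1 and s = 1 the bias falls to 0.12/0.09/0.05 at 80% retention and 0.06/0.05/0.03 at 90%. With s = 0 it is zero.

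**5. Mixed model on all enrolled.** Simulation used 40,000 runs per case, at 65% and 80% retention.
- Unstructured covariance: bias at most 0.004.
- Root mean squared error relative to the paired estimate: 0.928 to 1.041 for k = 1, and 0.991 to 1.128 for k = 1.3.
- A random-intercept model, which forces equal SDs, was biased by up to 0.08 at k = 1.3. The covariance structure therefore needs stating.
- If dropout depends on the unseen post value (k = 1, 65% retention), both are biased: paired 0.05 to 0.20, mixed 0.08 to 0.27.

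**6. What REML changes.** In a two-visit unstructured model with only post values missing, the likelihood factorises and ML and REML give the same mean change. REML affects the error bars; using all enrolled participants is what removes the bias.

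**The case against.** The strongest reply is that the plan already contains the remedy. It expects attrition, includes a likelihood-based mixed model, and states missing at random for it. The words *first* and *also* may describe sequence only. The main strategy is descriptive, p-values are set aside, and showing both analyses is reasonable in a pilot. All of that stands. What remains is that neither estimate is named as the one to use.

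The second reply is that the mixed model is not clearly the better estimator. Its root mean squared error runs from 7% lower to 13% higher under random or baseline-dependent dropout, and it is the more biased of the two if dropout depends on the post value. The poorer end belongs to unequal SDs. Those are plausible for patients' pain, because entry restricts baseline scores to at least 4 and below 9 while post scores are unrestricted. This also stands: the argument for the mixed model is consistency with the plan's own missing-data assumption, not precision.

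Third, the paired t-test already divides by n − 1. The ML point therefore concerns the second analysis only.

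Four stronger readings are tempting, and the documents do not support them:
- *The plan makes a completers-only test its principal analysis and ignores dropouts.* It does not rank the two analyses.
- *The planned confidence intervals will under-cover.* No interval is specified.
- *Effect sizes will be inflated by the ML divisor.* Nothing says they will be scaled by the ML variance.
- *The plan overlooks correlation within yoga groups.* Study Design raises it and says "we have very limited ability to estimate the ICC, or the component of variance associated with the group or yoga teacher".

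**Conclusion.** The concern holds in a limited form and is minor. At 15 per role, the stated ML fit makes the variance of change about 7 to 10% low with complete pairs and 5 to 8% low in simulated fits with dropout. This follows from the sample size and the fitting method, whatever the reason for dropout.

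The bias in the completers-only estimate is conditional. It rests on assumed dropout slopes, correlations and SD ratios, and on retention at the 65% aim, which is a floor and not a forecast. Within those assumptions it is 0.01 to 0.20 baseline SD, below one standard error throughout.

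A reader might infer that changing ML to REML would correct the estimated change, or that the feasibility conclusions are in doubt. Neither follows. REML leaves the unstructured point estimate as it was, and the adherence and satisfaction hypotheses under Objectives use neither analysis.

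**What to change.** In Statistical Plan and Data Analysis, replace the reference to maximum likelihood with wording such as:

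> Change will be estimated separately for patients and caregivers from a mixed model for the baseline and post-treatment values of all enrolled participants with at least one assessment. The model will have unstructured covariance and be fitted by restricted maximum likelihood with Kenward-Roger or Satterthwaite degrees of freedom. This is the estimate of change carried forward. The paired t-test will be reported as a completers-only sensitivity analysis, with its n.

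Of the two adjustments, Kenward-Roger also enlarges the standard error; Satterthwaite changes the degrees of freedom only.

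The cost is a few sentences and a software option. Error bars become slightly wider, there is no reliable gain in precision, and the mixed model offers no protection if dropout depends on the unseen post value. That last limit is the reason to keep the completers' result alongside it.

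Before this can be applied to pain, two places must be reconciled: the analysis section names change in DVPRS, while Table 2 lists DVPRS at screening only. BDI-II, by contrast, is listed at baseline and post-treatment.

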Individual sessions: Yoga will be first be provided individually. That is, yoga sessions will include the yoga therapist, one AD patient and one caregiver. We will recruit n=5 dyads (5 AD patients, 5 caregivers).

Group sessions: The study will also demonstrate the feasibility of providing group yoga. Feasibility will be measured for recruitment, retention, and adherence. We will recruit n=10 dyads (10 AD patients, 10 caregivers). When the required number of participants have been identified, the study team will schedule baseline assessments. After the baseline assessment, the cohort will receive group yoga. We currently estimate that due to technical limitations of

instructing yoga via videoconferencing, the largest group size will be 10 participants. Since this is a feasibility study, the study is not powered for efficacy.

Yoga Intervention: We will adapt the yoga protocol from the active award. The protocol is 12 weeks in duration, 1 class/week, class length of 75 minutes, with additional homework 15-20 mins on 5 non-class days/week. The protocol uses seated/standing/supine yoga postures, breathing, and meditation, and contains standard modifications in cases of limited mobility. Participants will also receive a homework manual describing simple and safe exercises to practice for homework.

The sample size (n=15) is small, but will provide the necessary information on recruitment, adherence, acceptability and self-report measures of pain and pain-related function to plan a larger fully powered efficacy study in the future. Developing a yoga intervention for groups is typical of yoga interventions, as it allows a small staff to treat many individuals simultaneously.

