- Has a caregiver who is willing to accompany AD patient for treatment, and who can receive yoga treatment at the same time as AD patient.

Exclusion Criteria for AD patients (As determined by):

- Participation in another concurrent clinical trial
- Back surgery within the last 12 months

- Back pain potentially attributed to a specific underlying cause, disease, or condition (VA EMR; screening interview)
- Baseline pain <4 or ≥9 on a 0-10 Numeric Rating Scale (NRS)

Inclusion Criteria for CAREGIVERS of AD patients (As determined by):

- Are caring for a patient diagnosed with AD who will practice yoga together with them
- Has a primary care provider who can provide medical clearance for participation in the study (Yoga Medical Clearance Form)
- Exclusion Criteria for Caregiver
- Participation in another concurrent clinical trial
- Attended or practiced yoga ≥ 1 x in the past 12 months
- Attended or practiced yoga ≥ 1 x in the past 12 months

Informed Consent Process

Participants will be recruited from four sources: Brain Health Registry, the VAPAHCS Pain Clinic, local advertising, and web-based advertising. These sources will result in either 1) the potential participant calling the study team or 2) with the participant's consent, the study staff contacting them directly. Study candidates will be invited to VAPAHCS for a screening visit, during which the Project Manager will obtain informed consent and review the Health Insurance Portability & Accountability Act (HIPAA) document.

The informed consent process will involve the AD patient and their caregiver together. They will complete separate consent forms. As we are enrolling AD patients with impaired consent capacity, the caregiver will act as a legal authorized representative (LAR) and provide consent for the AD patient, who will be asked to provide their assent. These forms will include the HIPAA document and are estimated to take about 60-90 minutes. It will take place in a quiet office or interview room, located in the same building as the PI, who will be available to answer any of the study candidate's questions.

1. The Project Manager will explain the information contained in the written informed consent forms (purpose, procedures, risks, benefits, alternatives to participation, etc.) and HIPAA documents to the study candidates verbally, in lay language.

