Clinical Questionnaire: Self-report document focusing on the existence of 78 health symptoms taken from a list of ICD-9 codes that are highly likely to represent chronic pain.

Medication Use: Self-report of all current pharmacological and non-pharmacological treatments.

Yoga Home Practice Log: Log for participant to document their yoga home practice on non-treatment days.

BDI-II Beck Depression Inventory-II (BDI-II): Contains 21 self-report questions, scored on a 0-3 scale, related over the past two weeks to sleep, appetite, punishment, suicide, and interest in sex.

Brief Pain Inventory-Short Form (BPI-SF): Assesses intensity and impact of pain on functioning on a 0-10 rating scale. Interference is assessed on daily life (general, walking, work, mood, enjoyment, relationships, sleep). The BPI is recommended by the Initiative on Methods, Measurement, and Pain Assessment in Clinical Trials (IMMPACT) group for inclusion in clinical trials evaluating pain.

Defense and Veterans Pain Rating Scale (DVPRS): A five-item scale: one 0-10 pain intensity numeric rating scale and four supplemental items measuring functional outcomes (general activity, sleep, mood, level of stress). The pain intensity scale is designed to improve upon

existing scales by using visual cues and word descriptors to anchor pain ratings with perceptual experiences and limitations imposed by pain.

PEG: A 3-item pain measure derived from the Brief Pain Inventory and validated in ambulatory care settings. It includes 1 severity item (average pain) and 2 interference items (enjoyment of life and general activity).

Pittsburg Sleep Quality Index (PSQI) (62): Contains 10 self-report questions regarding sleep habits over the past month, including discrete responses (e.g. amount of sleep) and responses scored on a 0-3 scale (“not during the past month” to “three or more times per week”), related to sleep quality, medication use, motivation, and fatigue. A global sum score indicates level of sleep difficulties.

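### Clinical significance is equated with effect size, with no standardiser named and no confidence interval promised for 10 to 15 pairs

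*Combined protocol and SAP*

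**What the plan says.** The Statistical Plan and Data Analysis section opens with a descriptive aim: "The main analytic strategy will be descriptive statistics for pre- and post-intervention assessments for AD patients and their caregivers". For AD patients, "we will estimate changes in pain (DVPRS), depression (BDI-II), sleep (PSQI) and cognition (CanTab"). For every change analysis, "we will first employ simple paired t-test (pre vs. post) given the correlation between pre and post measures", followed by a mixed model fitted by maximum likelihood. The section closes with the rule at issue, which covers all analyses: "we will focus on collecting preliminary data on clinical significance (i.e., effect size) instead of making formal inference (i.e., p-value").

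The documents give no effect-size formula, choice of SD, important change or responder threshold, and they name no confidence interval for any outcome. The only interval in them belongs to a review cited in the Background.

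Three other places bear on the point:

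- **Pain at entry.** AD patients need at least 4 at screening, and the exclusion criteria remove "Baseline pain <4 or ≥9 on a 0-10 Numeric Rating Scale (NRS"). In whole points that leaves 4 to 8.
- **Outcome scale.** Study Assessments describes the DVPRS as "one 0-10 pain intensity numeric rating scale and four supplemental items measuring functional outcomes".
- **Use of the results.** Study Design, under Yoga Intervention, says the 15 dyads will supply information, including on pain, "to plan a larger fully powered efficacy study in the future".

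**The concern.** Two separate faults sit in one sentence.

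The first is conceptual. A standardised effect measures change against spread between people, or against spread in their changes. A change too small for patients to notice can give a large value if the sample is homogeneous, and a worthwhile change can give a small value if it is not. Clinical significance needs a change in scale points set beside a change that has been judged important. With no SD named, the value is not even determined: the same data give several answers. For pain one candidate, the baseline SD, is narrowed by the entry criteria, while post-treatment scores may fall anywhere from 0 to 10.

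The second is imprecision. The plan sets p-values aside, which is sensible for a feasibility study, but it does not commit to reporting an interval in their place. A bare point estimate from 10 to 15 pairs invites over-reading by whoever plans the next trial.

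An interval would not cure the first fault, and naming the SD would not cure the second.

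**Working it through.** The plan states no effect size, SD or expected change, so there is no figure to reproduce. What follows shows how far the reported value could move.

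**Inputs from the documents.** Entry window 4 to 8 on a 0-10 scale; 15 dyads; retention target 65%, so 0.65 × 15 = 9.75, about 10 pairs.

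**Assumptions, not in the documents.** Mean change 1 point; pain SD without the window 2.0, with mean 5 to 6; pre-post correlation r = 0.7, varied from 0.3 to 0.8; entry NRS and outcome scale treated as the same.

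**Step 1: baseline SD inside the window.** A rounded normal score on 0-10 with SD 2 and mean 5 or 6, restricted to 4-8, has SD 1.26 or 1.29. I use 1.27. Scores spread evenly over 4-8 would give 1.41, and the population maximum is 2.0 (half at 4, half at 8). Over assumed means 4 to 7 and SDs 1.5 to 3, the windowed SD runs from 0.97 to 1.36, so 1 point reads 1.03 down to 0.74 on that divisor.

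**Step 2: the other two SDs.** With a linear pre-post relation of slope r and residual variance (1 − r²) × 2.0²:

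- Post variance = r² × 1.27² + (1 − r²) × 4. At r = 0.7: 0.49 × 1.613 + 0.51 × 4 = 2.83, SD 1.68.
- Change variance = (1 − r)² × 1.27² + (1 − r²) × 4. At r = 0.7: 0.09 × 1.613 + 2.04 = 2.19, SD 1.48.

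**Step 3: a 1-point change on each SD that this trial can observe.**

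| r | post SD | SD of change | baseline SD |
|---|---|---|---|
| 0.3 | 1/1.95 = 0.51 | 1/2.11 = 0.48 | 1/1.27 = 0.79 |
| 0.5 | 1/1.84 = 0.54 | 1/1.84 = 0.54 | 0.79 |
| 0.7 | 1/1.68 = 0.59 | 1/1.48 = 0.68 | 0.79 |
| 0.8 | 1/1.57 = 0.64 | 1/1.23 = 0.82 | 0.79 |

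The ordering changes with r. At 0.3 the SD of change gives the smallest value, at 0.8 the largest.

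**Step 4: imprecision.** Noncentral-t 95% CI for an observed paired effect (mean change / SD of change) of 0.5: -0.17 to 1.15 with 10 pairs, -0.05 to 1.03 with 15. In points, the half-width is t × SD of change / √n. With SD 1.48 that is 2.262 × 1.48/√10 = 1.06 points for 10 pairs and 2.145 × 1.48/√15 = 0.82 for 15. The planning inputs are also loose: the 95% CI for an SD runs from 0.69 to 1.83 times the estimate with 10 pairs, and from 0.73 to 1.58 times with 15.

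**Step 5: regression to the mean.** Under the same model, change expected with no treatment effect is (1 − r) × (mean in window − unrestricted mean). With unrestricted mean 5.0 the windowed mean is 5.60, giving 0.3 × 0.60 = 0.18 points of apparent improvement. With unrestricted mean 5.94 the windowed mean is 6.00, giving 0.02. It is small here because the upper exclusion partly offsets the lower one, but a single arm cannot separate it from benefit.

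**The case against.** The strongest reply is that this is a feasibility study with hypotheses on adherence and satisfaction. It is expressly not powered for efficacy, its main strategy is descriptive, and the paired t-test and mixed model both yield a change in points with a standard error. That stands in large part. It rules out saying that the plan discards every measure of uncertainty: the material for an interval will exist, and what is missing is a commitment to report it.

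Three stronger readings are tempting, and the documents do not support them.

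- **A reader might infer a spread of 0.5 to 0.8 SD.** The 0.50 end is 1/2.0, using the SD of an unselected population. A sample admitted only at 4 to 8 does not supply that SD.
- **A reader might infer that the next trial will be too small**, for example 27 per arm at 0.79 SD against 64 at 0.50 (two-sided 5%, 80% power). But a future trial with the same window would not face SD 2.0. At r = 0.8 a baseline-adjusted comparison has residual SD √(0.36 × 4) = 1.20 and needs about 24 per arm, fewer than 27. At r = 0.5 it needs about 49, so the shortfall would be real. The direction depends on the correlation, the future analysis and the future entry rule, none of which is documented.
- **A reader might infer that the pilot's standardised effect will size that trial.** The plan says only that the results will help to plan it, and it ties the patient outcomes to target engagement and mechanism.

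Two further limits apply. The window concerns pain alone, not the depression, sleep, cognition or caregiver measures. And entry uses an NRS while the outcome is the DVPRS, so the narrowing carries over only as far as the two agree. Carry-over is likely, since the DVPRS contains a 0-10 intensity item and is listed in Screening Procedures, but it is not certain.

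**Conclusion.** The point holds as a fault of definition and reporting. The plan treats effect size as clinical significance, leaves the divisor open and promises no interval, in a sample of about 10 to 15 pairs meant to inform a powered trial. These are facts of the text and need no assumption.

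The size of the ambiguity for pain is illustrative: 0.59, 0.68 or 0.79 for one and the same 1-point change at r = 0.7, with the extremes moving to 0.48 and 0.82 as r runs from 0.3 to 0.8. It rests on the assumed change, SD and correlation, and on the NRS and the outcome scale behaving alike. The intervals for a paired effect of 0.5 depend only on the number of pairs and the usual normal model.

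No primary conclusion changes, and undersizing of the next trial is not shown. The sentence should still be changed, because the cost is close to nil.

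One dependency comes first. Table 2 marks the DVPRS at screening only, so the DVPRS change promised in the statistical section has no scheduled post-treatment value. The two places must be reconciled before any DVPRS change can be reported.

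**What to change.** In the Statistical Plan and Data Analysis section:

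1. Delete the parenthesis that defines clinical significance as effect size.
2. For each outcome, report mean change in scale points with a 95% CI from the planned paired analysis or mixed model. Judge it against a threshold in points that the sponsor fixes, with its source, before analysis.
3. If a standardised effect is also shown, name the SD used and give its 95% CI.
4. For planning, report the post-treatment SD and the pre-post correlation, each with a 95% CI.
5. State that single-arm change after selection on a minimum pain score of 4 includes regression to the mean and is not an estimate of treatment effect.
6. Reconcile the DVPRS change analysis with the DVPRS row of Table 2.

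This plan need not commit to how a later trial will be sized.

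Items 1 to 5 are wording only, with no new data or visits. Item 6 is also wording if a post-treatment DVPRS is already being collected or if the text is aligned to a pain measure that Table 2 schedules at baseline and post-treatment (BPI-SF, PEG or PROMIS-PI). Otherwise it adds one short form. The price is results that look less favourable and are visibly imprecise.
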